Study Protocol

Official Title: The effect of peri-surgery blue and amber light exposure in subjects undergoing medical and surgical treatment of cancer.

ClinicalTrials.gov ID (NCT number): 06164691

Protocol Date: Initial approval: 8/4/2022.

Scientific Background: The 5-year survival for pancreatic cancer (all SEER stages combined) is 11%; for those with Stage IV disease, fewer than 3% survive 5 years. Though the biology of this disease, specifically its chemoresistance and ability to evade immune defenses, is complex and just being elucidated, an emerging theme is the generation of neutrophil extracellular traps (NETS). There are now 7 basic, preclinical and translational studies highlighting the role of NETS in accelerating tumor growth, metastasis, and hypercoagulability; notably, in many of those studies methods to reduce NETS (e,g., administration of DNAse) are therapeutic, restoring innate and adaptive immunity in the tumor microenvironment and attenuating tumor growth.

https://pubmed.ncbi.nlm.nih.gov/?term=pancreatic+cancer%5BTitle%5D+AND+neutrophil+extra cellular+traps%5BTitle%5D&sort=date

For cancers in general, the list of publications is 75.

Undoubtedly there are mechanisms in addition to NETosis (i.e., generation of NETS) by which this cancer and others can thwart immunosurveillance, including dysfunction in immune cell (monocytes, macrophages, lymphocytes) antigen processing, MHC class I and II, and antigen presentation. Regardless there is immense interest and active research in developing methods to restore immune competence and even specifically targeted immunotherapy, for the treatment of a variety of cancers.

https://pubmed.ncbi.nlm.nih.gov/?linkname=pubmed_pubmed&from_uid=33750922

Related is the field of study entitled chronotherapy. More and more human observational and clinical trials underscore the relationship between circadian rhythms and outcomes agnostic to the specific disease of study. For cancer alone, there are now N=63 studies that highlight the dependence of medical and surgical outcomes in the treatment of cancer on the time of day at which the therapy is delivered.

https://pubmed.ncbi.nlm.nih.gov/?term=chronotherapy%5BTitle%5D+AND+cancer%5BTitle%5 D&sort=date

Specifically, the collective evidence for cancer have created a biological and clinical conceptual paradigm in which the delivery of therapy during the active circadian phase (i.e., day for diurnal mammals, night for nocturnal mammals) reduces the side effects from chemotherapy (e.g., gastrointestinal), enhances completion of the full chemotherapeutic regimen, and reduces tumor growth, metastasis, and survival. The circadian mechanisms regulating this benefit have yet to be defined. However, recent studies identify the importance of the circadian clock protein Rev-Erb α (NR1D1). In this studies, pharmacological enhancement of Rev-Erb α activity was observed to be lethal in cancer and oncogene senescence in cell and small animal based studies.1,2 The authors conclude that means by which to augment Rev-Erb α should be further studied in cancer biology and treatment.

https://pubmed.ncbi.nlm.nih.gov/?term=Rev-Erb%5BTitle%2FABstract%5D+AND+cancer%5BTitle%5D&sort=date

Within each cell is a circadian clockwork of proteins that dovetails with the molecular machinery regulating cell phenotype. These peripheral clocks are synchronized across the entire organism by the master central clock of the suprachiasmatic nucleus (SCN). Each day, light travels in

through the eve to the SCN, and via the autonomic nervous system (ANS), pineal gland, and hypothalamic-pituitary adrenal (HPA) axis, coordinates a temporal program of physiologies, such as enhancing immune competence. This system is maximally entrained by the short wavelength visible blue spectrum. Our lab has been studying circadian rhythms and clock biology for nearly a decade. We have applied blue light in 4 distinct models to reduce tissue injury: ischemia/reperfusion of the liver and kidney3, intraabdominal sepsis4, and pneumonia.5 In our studies of sepsis, we identified an optic-parasympathetic pathway through which blue light elevated the expression of the clock protein Rev-Erb α within the spleen and bolstered a splenic population of CCR2+ inflammatory monocytes.4,5 Tissue resident macrophages (e.g., the lung) also exhibited increased Rev-Erb α in mice exposed to blue light. This enhanced bacterial clearance and increased survival 4-fold. Notably, a Rev-Erb α agonist (SR9009) replicated the effects of blue light, augmenting bacterial clearance and prolonging survival, whereas mice deficient in Rev-Erb α were no longer protected by blue light, nor were mice that had undergone splenectomy.4,5 In both I/R and sepsis the enhanced immune competence was accompanied by reduced neutrophilic inflammation, the formation of NETS, and bystander tissue injury. More preliminary data from single cell RNA seg and gene ontology (GO) enrichment analyses direct our attention to unique populations of monocytes and B cells that emerge predominantly in mice exposed to blue light. From these data an innovative paradigm emerges, integrated at the molecular, cellular, and organismal levels, in which neurophysiologic pathways converge on the bone marrow and spleen and tissue resident immune cell population to set the clock protein machinery of immune cells to an 'active day,' characterized by elevated Rev-Erba. This recruits a highly functional population of monocytes enriched in Major Histocompatibility Complex class II (MHC II) and antigen presentation, Type I Interferon (IFN-I) responses, and cellular defense. This also induces development of a cluster of B cells, expressing a cluster of genes enriched in MHC II, actin assembly and associated signaling pathways, including PI3K-AKT, and immunoglobulin production. These support an immune cell phenotype vital to an efficient immune response to a variety of stimuli.

Our murine studies suggest that exposure to blue (442nm) light, by comparison to ambient white or amber (617nm) light, improves immune competence by augmenting immune cell Rev-Erbalpha expression and activity. A common theme in all of these preclinical models is an enhancement in immune competence with enhanced antigen processing, MHC class I expression, and antigen presentation; reduced neutrophilic inflammation and NET formation, and enhanced competence of mononuclear cells when animals or humans are exposed to blue light. Note that these physiological and biological pathways induced by blue light appear to converge on Rev-Erb α , and in preclinical studies, a Rev-Erb α agonist (SR9009), the same used in the aforementioned studies of cancer, perfectly replicated the effects of blue light (see references below). These are directly relevant to the current focus of this IRB application on cancer.

The ability to enhance the host response/tolerance to chemotherapy and major operations and directly augment the immune response to the cancer itself offers immense potential to improve patient care. Importantly, the risk of light is minimal; we and others have never identified an adverse event in either mice or humans exposed to bright blue light. Thus, the intervention of exposing a patient to a characteristic spectrum of light carries a very large benefit:risk ratio. The results of these studies may be directly applicable to a more generalized population of patients being treated for cancer.

Randomized Controlled Trial Crit Care Med. 2018 Aug;46(8):e779-e787. doi: 10.1097/CCM.00000000003190.

Blue Light Enhances Bacterial Clearance and Reduces Organ Injury During Sepsis https://pubmed.ncbi.nlm.nih.gov/29727369/ https://pubmed.ncbi.nlm.nih.gov/?term=blue+light+AND+[name]&sort=date

1 Shen, W. et al. SR9009 induces a REV-ERB dependent anti-small-cell lung cancer effect through inhibition of autophagy. Theranostics 10, 4466-4480, doi:10.7150/thno.42478 (2020). 2 Sulli, G. et al. Pharmacological activation of REV-ERBs is lethal in cancer and oncogene-induced senescence. Nature 553, 351-355, doi:10.1038/nature25170 (2018).

3 Yuan, D. et al. Blue light reduces organ injury from ischemia and reperfusion. Proc Natl Acad Sci U S A, doi:10.1073/pnas.1515296113 (2016).

4 Lewis, A. J. et al. Blue Light Enhances Bacterial Clearance and Reduces Organ Injury During Sepsis. Crit Care Med, doi:10.1097/CCM.000000000003190 (2018).

5 Griepentrog, J. E. et al. Frontline Science: Rev-Erbalpha links blue light with enhanced bacterial clearance and improved survival in murine Klebsiella pneumoniae pneumonia. J Leukoc Biol, doi:10.1002/JLB.4HI0519-155R (2019).

Study Objectives: The primary purpose of this study is to test whether exposure to blue (442nm) light or amber (617nm) light, by comparison to ambient white fluorescent light, improves 1) the immune and oncological response to neoadjuvant chemoradiation therapy; 2) side effects and toleration to neoadjuvant chemoradiation therapy; 3) sleep (PSQI), pain control (BPI), functional status (Karnofsky), and quality of life (WHOQOL-BREF); and 3) survival in patients with 1) pancreatic cancer and 2) rectal cancer.

We incorporate appropriate control subjects: subjects matched by cancer type, stage, and age who undergo the same medical and surgical best practice care but are not exposed to any modulation of environmental light (i.e. ambient white fluorescent light).

We will analyze the blood (10mL) isolated from subjects for the following parameters: 1) monocyte function; 2) inflammatory markers; and 3) circadian clock markers. We will assess the following clinical outcomes of interest: 1) tolerance of neoadjuvant chemotherapy and radiation therapy; 2) sleep (PSQI), pain control (BPI), functional status (Karnofsky), and quality of life (WHOQOL-BREF); 3) clinical and pathological complete response; and 4) all-cause survival.

We hypothesize that exposure to blue (442nm) spectrum light, by comparison to amber and ambient light, induces monocyte Rev-Erb alpha expression, improves tolerance of neoadjuvant chemoradiation therapy (e.g., reduced gastrointestinal complications), increases completion of the full neoadjuvant chemoradiation therapy, improves quality of sleep and quality of life, augments the biological (i.e., reduced NETS in the blood and specimen) and oncological response (i.e., greater rate of complete response) to neoadjuvant chemoradiation therapy and improves survival.

Study Design & Methods: Total number of subjects to be enrolled at this site: 238. This study is an experimental investigation of exposure to blue (442nm) light, amber (617nm) light, or ambient white light in subjects undergoing neoadjuvant chemoradiation therapy and/or surgery for either pancreatic cancer or rectal cancer.

It is an open-label, unblinded, prospective study. There are six (6) different groups with two (2) different cancers and three (3) different lighting conditions.

There are a total of six (6) groups:

Pancreatic Cancer

1. Group 1 cohort will be exposed to bright (1700 lux) blue (peak 442 nm) light for 4 hours each morning for 3 days prior to and 3 days following each chemotherapy infusion. They will be exposed to bright (1700 lux) blue (peak 442 nm) light for 1 hour each morning during radiation treatments.

2. Group 2 will be exposed to bright (1700 lux) amber (peak 617 nm) light for 4 hours each morning for 3 days prior to and 3 days following each chemotherapy infusion. They will be exposed to bright (1700 lux) amber (peak 617 nm) light for 1 hour each morning during radiation treatments.

3. Group 3 will be exposed to usual, ambient white lighting of the environment during chemotherapy and radiation treatments.

Rectal Cancer

4. Group 1 cohort will be exposed to bright (1700 lux) blue (peak 442 nm) light for 4 hours each morning for 3 days prior to and 3 days following each chemotherapy infusion. They will be exposed to bright (1700 lux) blue (peak 442 nm) light for 1 hour each morning during radiation treatments.

5. Group 2 will be exposed to bright (1700 lux) amber (peak 617 nm) light for 4 hours each morning for 3 days prior to and 3 days following each chemotherapy infusion. They will be exposed to bright (1700 lux) amber (peak 617 nm) light for 1 hour each morning during radiation treatments.

6. Group 3 will be exposed to usual, ambient white lighting of the environment during chemotherapy and radiation treatments.

Randomization will achieved with block randomization on the following characteristics:

a. Type of cancer: group 1: pancreatic cancer; group 2: rectal cancer

b. Stage of cancer as defined by Tumor Node Metastasis classification

b. Age (<55 years, >/= 55 years)

Eligibility Criteria:

Inclusion criteria:

1. greater than 18 and less than 65 years of age

2. adenocarcinoma of the pancreas (unresectable) or adenocarcinoma of the rectum (stage II or III)

Exclusion criteria:

 Prior chemotherapy (inability to determine the integrity of the immune response)
Autoimmune disorder, immunosuppression therapy, or immunocompromised state (inability to determine the integrity of the immune response)

Blindness or other significant vision disorder or prior traumatic brain injury (the inability to determine the integrity of functional optic and suprachiasmatic pathways)
Hematological disease - e.g., myelodysplastic syndrome, leukemia (inability to determine the integrity of the immune response)

5. Bipolar disorder or schizophrenia (potential heightened symptoms)

6. Refusal/ineligible to undergo neoadjuvant chemotherapy and/or radiation

Statistical Considerations:

1. Survival:

a. Assuming a median survival of 198 days for patients with stage IV pancreatic cancer who undergo chemotherapy, a two-sided alpha=0.05, and beta=0.20 (power of 80%), we will need n=36 participants in each group to detect an effect size of a Hazard Ratio of 2 for all-cause survival (doubling in survival rate).

2. Biological Parameters:

b. The recruitment of n=36 participants into each group will enable us to detect the following difference in proportion of participants experiencing a >90% reduction in serum CA19-9 and CEA concentrations: 23% vs. 55%.

We do anticipate approximately 10% attrition, and thus, will include a total of N=238 subjects into this study.

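### The 80% survival power at n=36 per group is derived only for stage IV pancreatic cancer; nothing supports it for stage II–III rectal cancer, and the pancreatic analysis has no set time

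*Combined protocol and SAP*

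**What the plan says.** All of this is in the combined protocol and SAP.

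- **Statistical Considerations, 1. Survival.** The premise is "Assuming a median survival of 198 days for patients with stage IV pancreatic cancer who undergo chemotherapy". With two-sided alpha 0.05 and 80% power, the conclusion is "we will need n=36 participants in each group to detect an effect size of a Hazard Ratio of 2 for all-cause survival". The effect is glossed as a doubling in survival rate.
- **Statistical Considerations, 2. Biological Parameters.** A second basis for the same number: "The recruitment of n=36 participants into each group will enable us to detect the following difference in proportion of participants" with a reduction of more than 90% in CA19-9 and CEA, 23% versus 55%.
- **Statistical Considerations, closing sentence.** "We do anticipate approximately 10% attrition, and thus, will include a total of N=238 subjects into this study".
- **Study Design & Methods.** "There are six (6) different groups with two (2) different cancers and three (3) different lighting conditions". Cancer type is a blocking factor in the randomization ("Type of cancer: group 1: pancreatic cancer; group 2: rectal cancer").
- **Eligibility Criteria, inclusion 2.** "adenocarcinoma of the pancreas (unresectable) or adenocarcinoma of the rectum (stage II or III".
- **Study Objectives.** The primary purpose includes "3) survival in patients with 1) pancreatic cancer and 2) rectal cancer".

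No rectal survival rate, median, death count or power is given. For neither cancer is there an accrual period, a follow-up length, a target number of deaths or an analysis time.

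**The concern.** The premise of the survival calculation is restricted to one disease and stage; its conclusion, n per group, is not. That number is then carried into a six-group design in which half the groups have a different cancer at an earlier stage. Power for a survival comparison comes from deaths, not from patients enrolled, so a sample size that works when almost everyone dies cannot be transferred to a population whose death rate is not stated.

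Two things are at stake. A null rectal survival result could be read as coming from an 80%-powered comparison when no such power was derived. And in pancreatic cancer, where the calculation does apply, the 80% depends on how long patients are followed. The plan leaves that open in an unblinded study.

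**Working it through.** **Inputs from the documents.** Hazard ratio (HR) 2; two-sided alpha 0.05 (z = 1.960); power 80% (z = 0.842); 36 per group; six groups; 10% attrition; N = 238; control median 198 days. Inferred: equal allocation, and comparison of two lighting conditions within one cancer (72 patients, or 238/3 = 79.3 if everyone enrolled contributes). The documents describe no survival analysis, so the within-cancer pair rests on the six-group layout and the two-cancer objective.

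**1. Reproducing the plan's figures.**
- Freedman: (1.960 + 0.842)² × [(2 + 1)/(2 − 1)]² = 70.64, so 71 deaths. 71/2 rounds up to 36 per group if essentially everyone dies. This matches the plan.
- Schoenfeld: 4 × (1.960 + 0.842)² / (ln 2)² = 65.35, so 66 deaths.
- Total: 6 × 36 = 216, and 216 × 1.10 = 237.6, so 238. The 36 is used in all six groups.
- Marker comparison, 23% vs 55%, 36 per group, pooled z test: power 80.8%.

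**2. Deaths needed as a share of patients.**

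| Patients in the pair | 66 deaths | 71 deaths |
|---|---|---|
| 72 | 91.7% | 98.6% |
| 79.3 (all enrolled) | 83.2% | 89.5% |

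**3. Control survival that this implies.** With n per group, control survival S at analysis and HR 2, expected deaths are D = n[(1 − S) + (1 − √S)]. Setting D = 65.35:
- n = 36: S + √S = 2 − 1.815 = 0.185, so S is about 2.5%.
- n = 39.7: S + √S = 2 − 1.648 = 0.352, so S is about 7.6%.

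Control survival must be no higher than this for 80% power.

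**4. Rectal power if fewer die.** Power = Φ(√(D/4) × ln 2 − 1.96). The death fractions below are assumptions, not in the documents, and apply to both groups of a 72-patient pair together.
- 50% dead: D = 36.0; √9.0 × 0.693 − 1.96 = 0.12; power 55%.
- 30% dead: D = 21.6; √5.4 × 0.693 − 1.96 = −0.35; power 36%.

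**5. Pancreatic power over time.** Exponential survival, medians 198 and 396 days (the stated median and HR 2 read as a halved hazard), with the same follow-up for every patient:

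| Follow-up per patient | Deaths, 36 per group | Power | Deaths, 39.7 per group | Power |
|---|---|---|---|---|
| 1 year | 43.0 | 62% | 47.4 | 66% |
| 2 years | 59.2 | 76% | 65.2 | 80% |
| 3 years | 65.9 | 80% | – | – |

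With 36 per group, 66 deaths are expected at about 1,101 days and 71 at about 2,063 days.

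**6. Multiplicity.** Each cancer has three lighting conditions, hence up to three pairs, and no adjustment is described. At 66 deaths, √16.5 × 0.693 = 2.816. Power is Φ(2.816 − 1.960) = 80% unadjusted, Φ(2.816 − 2.241) = 72% if alpha were split over two comparisons, and Φ(2.816 − 2.394) = 66% over three.

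**The case against.** The strongest reply is that the survival sentence names its own population, and no sentence claims 80% survival power in rectal cancer. The marker comparison also yields 36 per group, so the total of 238 follows without applying the survival calculation to rectal patients. This is largely fair. That the statement extends to all six groups is an inference from its conclusion and from the total; strictly, the fault is an unlimited conclusion and a missing power statement. But marker power supplies no survival power, and nothing in the text marks rectal survival as unpowered or exploratory.

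Second, an analysis stratified by cancer could pool both diseases: 66 to 71 deaths would then be 46–49% of 144 patients. No such analysis is described, and it would answer a combined question rather than the rectal one.

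Third, with a 198-day median most pancreatic patients will die, so timing may seem moot. A high death fraction is indeed plausible, and the consequence is modest if follow-up reaches two to three years. The plan does not commit to that. Eligibility is also unresectable disease rather than stage IV, so the 198 days may not describe all pancreatic participants; the documents do not allow the size of that effect to be given.

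A reader might go further and infer that n=36 is miscalculated, that the trial has no valid sample-size basis, or that rectal survival power is known to be low. The documents support none of these: 36 reproduces, the marker comparison supports it separately, and actual rectal power cannot be computed without a rectal death rate.

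**Conclusion.** The concern holds as a matter of scope and timing. From the stated inputs alone, 80% power for HR 2 requires control survival at analysis of at most about 2.5% (7.6% if all enrolled contribute), and the documents offer nothing to support that in stage II–III rectal cancer. The 55% and 36% figures illustrate the sensitivity and rest on assumed death fractions. For pancreatic cancer the stated 80% is attainable, but only for a single unadjusted comparison analysed at about 66 deaths: roughly three years of follow-up per patient with 36 per group, or two if all enrolled contribute, assuming exponential survival at the stated median. It should be fixed. Confidence is high on the arithmetic and on what is missing, and lower on how readers will take the phrase about each group.

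**What to change.** 1. Limit the statement of n=36, HR 2 and 80% power to the pancreatic groups. Say that it is for one pairwise comparison without multiplicity adjustment and needs about 66–71 deaths, and give the lower power (about 72% or 66% at 66 deaths) that would apply if alpha were split over two or three comparisons. Express the effect as a halved hazard, with the median going from 198 to 396 days.
2. State that n=36 was not derived for rectal survival. Give the power at HR 2 under a declared rectal survival assumption, and label rectal survival exploratory, so that a null result is not reported as coming from an 80%-powered comparison.
3. State when the pancreatic survival analysis takes place: at about 66 deaths per comparison or at a latest calendar date, whichever comes first, with the power restated if the date comes first. If only 36 per group contribute, 71 deaths would mean 71 of 72 patients, so 66 is the workable target.

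The cost is protocol wording, with no extra patients. The stated power for rectal survival becomes less favourable, and the pancreatic analysis date depends on deaths up to the latest date.

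### Each cancer has three light contrasts, but n=36 per group is one two-group calculation, with no primary endpoint, contrast or success rule, and it is not justified for blue beating both comparators or for rectal survival

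*Combined protocol and SAP*

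**What the plan says.** - **Design** (Study Design & Methods): "There are six (6) different groups with two (2) different cancers and three (3) different lighting conditions". Each cancer therefore has three pairwise light contrasts.
- **Primary purpose** (Study Objectives): to "test whether exposure to blue (442nm) light or amber (617nm) light, by comparison to ambient white fluorescent light, improves" a list of outcomes covering immune and oncological response, tolerance of treatment, sleep, pain, function, quality of life and survival. The controls receive the same care "but are not exposed to any modulation of environmental light (i.e. ambient white fluorescent light". The contrasts here are blue vs ambient and amber vs ambient.
- **Hypothesis** (same section): "We hypothesize that exposure to blue (442nm) spectrum light, by comparison to amber and ambient light, induces monocyte Rev-Erb alpha expression", followed by clinical benefits up to survival. The contrasts here are blue vs amber and blue vs ambient.
- **Survival sample size** (Statistical Considerations, item 1): "Assuming a median survival of 198 days for patients with stage IV pancreatic cancer who undergo chemotherapy", with "a two-sided alpha=0.05, and beta=0.20 (power of 80%), we will need n=36 participants in each group" for a hazard ratio of 2.
- **Marker sample size** (item 2): the same 36 is said to "detect the following difference in proportion of participants experiencing a >90% reduction in serum CA19-9 and CEA concentrations: 23% vs. 55"%.
- **Total**: 238 after about 10% attrition.
- **Population** (Eligibility Criteria): "adenocarcinoma of the pancreas (unresectable) or adenocarcinoma of the rectum (stage II or III").

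No sentence names a primary endpoint, ranks the contrasts, or says whether one or both must succeed. No follow-up time, target number of deaths or survival assumption for rectal cancer is given.

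**The concern.** The sample size answers one question: do two groups differ? The design asks up to three such questions in each cancer, on many outcomes, and the two sentences that state the aim do not ask the same ones. In an open-label study without a rule, the contrast and endpoint that count can be settled after the data are seen.

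The missing rule also determines what the stated 0.05 and 80% mean. If any one significant contrast can support a claim, 0.05 describes each comparison and not the claim. If blue must beat both comparators, error is controlled but power falls below 80%. Half of the sample has rectal cancer, for which the survival calculation supplies no input.

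**Working it through.** **1. Reproduce the plan's figures.** Inputs from Statistical Considerations: two-sided alpha 0.05 (z = 1.960), power 80% (z = 0.842), hazard ratio (HR) 2.

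- Freedman: deaths = (1.960 + 0.842)² × [(1 + HR)/(1 − HR)]² = 7.849 × 9 = 70.6, i.e. 71. That is 36 per group if nearly everyone dies, which matches the plan.
- Schoenfeld: deaths = 4 × 7.849/(ln 2)² = 65.3, i.e. 66, or 33 per group, which does not match.
- Total: 6 × 36 = 216; 216 × 1.10 = 237.6, i.e. 238.
- Marker item: 23% vs 55% with 36 per group has about 81% power as one two-group test (alpha 0.05 assumed, since item 2 states none).

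So one pairwise calculation was carried to all six groups.

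**2. False-positive rate when each contrast is tested at two-sided 0.05.** Three equal groups; contrasts that share a group correlate at 0.5 in size. Simulated z-statistics with no true differences, per cancer and per endpoint:

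| Contrasts | Any significant difference | Favourable only (nominal 2.5%) |
|---|---|---|
| Two | 9.1% | 4.5% |
| Three | 12.2% | 6.6% |

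**3. Power for blue beating both.** Two z-statistics with correlation 0.5, both above 1.960, HR 2 for blue against each comparator. Expected z with 72 deaths per pair is √72/3 = 2.83 (Freedman) or √(72/4) × ln 2 = 2.94 (Schoenfeld).

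| Assumption | One contrast | Both |
|---|---|---|
| Amber = ambient, each contrast at exactly 80% | 80.0% | 68.7% |
| Amber = ambient, Freedman, 72 deaths | 80.7% | 69.7% |
| Amber = ambient, Schoenfeld, 72 deaths | 83.7% | 73.8% |
| Amber with half of blue's log-hazard benefit (assumed) | – | 27-30% |

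Log-rank simulation with all deaths observed gives about 71% for both in the amber = ambient case.

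**4. Are nearly all deaths observed?** With exponential survival, medians 198 and 396 days and follow-up of t days per participant, expected deaths = 36 × [(1 − 0.5^(t/198)) + (1 − 0.5^(t/396))].

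- 2 years: about 59 of 72; one-contrast power 73% (Freedman) to 76% (Schoenfeld).
- 3 years: about 66 of 72; 77% to 80%.

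**5. Rectal survival at HR 2, 36 per group.** The documents give no death proportion, so 20-50% is an assumed range.

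- 20-50% of both groups pooled: 14.4 to 36 deaths. Freedman 24-52%, Schoenfeld 26-55%.
- 20-50% of controls, with survival in the blue group equal to the square root of control survival: 11.0 to 28.5 deaths. Freedman 20-43%, Schoenfeld 21-46%.

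**6. Candidate procedures** (each contrast at 80% alone, amber = ambient).

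- Global three-group test, then pairwise tests, all at 0.05: family-wise error 5.0% in the normal model and about 5.7% in log-rank simulation at n=36. Power is 75.7% for blue vs ambient and 68.1% for blue beating both.
- Fixed order blue–ambient, blue–amber, amber–ambient: 80% for the first step and 68.7% for the first two together.
- Fixed order blue–ambient, amber–ambient, blue–amber: the third step is reached and significant only 1.8% of the time.

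**The case against.** **The arithmetic is sound.** This stands. The 36 is correct for one contrast with nearly complete deaths; what is at issue is how far it reaches.

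**The plan does not claim what it fails to deliver.** This also stands. A reader might infer that the plan promises 80% power for blue beating both comparators, or for rectal survival, and misstates it. It does not: the 80% is attached to one hazard ratio with a stage IV pancreatic input, and no family-wise error claim is made. The fault is that the same 36 is used for those purposes without justification.

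**Multiplicity control is partly a matter of judgement.** Two different lights against a shared control need not always be corrected, and favourable-only error of 4.5-6.6% is modest. But the protocol never calls itself exploratory; it states a primary purpose, a directional hypothesis and a power. Even without any correction, it must say which contrast and endpoint decide. The error figures are per endpoint, so they leave out the choice among the many listed outcomes.

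**The hypothesis supplies the contrast.** Only in part. It names two comparators for blue without saying whether both must be met, and it omits amber vs ambient, which the primary purpose includes.

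**The rectal powers rest on assumed death proportions.** True. The absence of any rectal survival input does not depend on them.

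**Conclusion.** The concern holds. The n=36 is a single two-group survival calculation for stage IV pancreatic cancer, applied to a design with three contrasts in each of two cancers and no primary endpoint, contrast or success rule.

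The consequence depends on the missing rule. Accepting any contrast at 0.05 raises the chance of a false difference to about 9-12% per cancer and endpoint. Requiring blue to beat both gives about 69-70% power by the formula that reproduces the plan's 36 (74% by Schoenfeld), assuming amber does nothing and nearly all participants die; the figure is far lower if amber has a benefit of its own. The 80% for one contrast also depends on nearly complete deaths, and its 198-day input is for stage IV disease while pancreatic eligibility is defined only as unresectable. Rectal survival power, at roughly 20-55% over the assumed range, is unsupported.

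This should be settled before any comparative data are seen.

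**What to change.** For each cancer separately, name one primary endpoint and one procedure for the light contrasts, and label all other outcomes secondary or exploratory.

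- **Preferred:** a global three-group test at 0.05, then pairwise tests at 0.05 only if it is significant. This controls family-wise error for exactly three groups. Because the log-rank test is slightly liberal at n=36, permutation versions could be used.
- **Alternative:** a fixed order that matches the claim. To support blue beating both, test blue vs ambient, then blue vs amber, then amber vs ambient, each at 0.05 and only if the previous step is significant. The figure of about 70% must not be quoted for an order that puts amber vs ambient second.

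Restate power to match:

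- Give 80% for survival only for one contrast at the full 0.05 in pancreatic cancer, on condition that nearly all participants in it die during follow-up, and note the mismatch between stage IV and unresectable.
- Give about 68% (global test) or 69-70% (fixed order) for blue beating both, with the assumptions.
- For rectal cancer, restate survival power under stated death proportions, or name a primary endpoint that n=36 supports.

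**Cost:** one or two paragraphs and no extra patients. The global test lowers power for one contrast from 80% to about 76%. Under a fixed order, later contrasts are not confirmatory once an earlier one fails. Error is held per cancer, not across both. Neither option restores 80% for blue beating both; with two unadjusted tests and all deaths observed, that would take about 43-45 per group.

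### Is a total of 238 too small for 36 participants in each of six groups with about 10% attrition?

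*Combined protocol and SAP*

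**What the plan says.** The Statistical Considerations section sets the group size twice. For survival, at two-sided alpha 0.05 and 80% power, it states "we will need n=36 participants in each group to detect an effect size of a Hazard Ratio of 2 for all-cause survival". For the tumour-marker responses (23% versus 55%) it states "The recruitment of n=36 participants into each group will enable us to detect the following difference in proportion of participants". The section closes with the attrition allowance: "We do anticipate approximately 10% attrition, and thus, will include a total of N=238 subjects into this study".

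Study Design & Methods supplies the number of groups, "There are six (6) different groups with two (2) different cancers and three (3) different lighting conditions", and repeats the total: "Total number of subjects to be enrolled at this site: 238".

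The plan does not write out the product 216. It does not show how the allowance was applied, and it does not say whether the 10% is a share of those enrolled or an addition to the number required.

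**The concern.** The closing sentence presents 238 as the consequence of the attrition allowance. The usual way to protect a required number against loss is to divide by the proportion retained, because losses occur among those enrolled. Multiplying by one plus the loss rate is a familiar slip that always gives a smaller total. Here 238 matches the multiplication exactly and falls below the 240 that division gives.

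If that shortfall mattered, the trial would enrol to its stated total, lose the fraction it expected to lose, and end with fewer than 36 per group. The group size has little slack, so a reader could reasonably ask whether the 80% power is still met.

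**Working it through.** **Inputs.** 36 per group, two-sided alpha 0.05, 80% power, hazard ratio 2, 23% versus 55%, and approximately 10% attrition (all Statistical Considerations); six groups and a total of 238 (Study Design & Methods). Equal group sizes are assumed, since the same 36 is given for every group.

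**The plan's own total**

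- Base: 6 × 36 = 216.
- Addition of 10%: 216 × 1.10 = 237.6, rounded up to 238. This reproduces the stated figure, though the plan does not confirm that it was the route taken.
- Division by the retained share: 216/0.90 = 240, a difference of 2 (2/240 = 0.8%).

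**What 238 absorbs**

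- Losses covered: 238 − 216 = 22, and 22/238 = 9.24%.
- At exactly 10% loss among those enrolled: 238 × 0.90 = 214.2, or 214.2/6 = 35.7 per group on average, 0.3 below 36.

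**How many per group the stated inputs require before rounding**

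- Two proportions, pooled-variance normal approximation: n = [1.960 × √(2 × 0.39 × 0.61) + 0.842 × √(0.23 × 0.77 + 0.55 × 0.45)]² / 0.32² = 35.27, rounded up to 36.
- Hazard ratio 2, Freedman: events = (1.960 + 0.842)² × [(2 + 1)/(2 − 1)]² = 7.849 × 9 = 70.6, or 35.3 per group if every participant has an event, again rounded up to 36.

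Both requirements lie below 35.7. The 36 is itself a rounded-up figure, and the 0.3 lost at exactly 10% attrition comes out of that rounding.

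**Power before and after the allowance is used up**

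| Comparison (two-sided alpha 0.05) | 36 per group | 35.7 per group |
|---|---|---|
| 23% vs 55%, pooled normal approximation | 80.8% | 80.5% |
| Hazard ratio 2, Freedman, all have events | 80.7% | 80.4% |
| Hazard ratio 2, Schoenfeld, all have events | 83.7% | 83.4% |

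Every entry is above 80%, and the change is about 0.3 percentage points in each row.

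**The case for a change.** The best argument for correcting the figure is that attrition ordinarily means loss among those enrolled. On that reading 240 is the total that returns 36 per group at 10% loss, and the remedy would cost two participants, or none if the text said about 9%. That reading is the standard one and the division is correct. But the plan does not state that denominator, and it qualifies the rate as approximate. A 9.2% allowance is a fair instance of approximately 10%, and a forecast of attrition is uncertain by far more than 0.8 of a percentage point.

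A sharper form of the argument uses whole numbers. Since 238/6 = 39.67, an even spread is four groups of 40 and two of 39 (4 × 40 + 2 × 39 = 238). If the two groups of 39 were the ones compared, and each lost exactly 10%, 39 × 0.90 = 35.1 would remain in each. By the formulas above, power would be 79.8% for the proportions and 79.8% by Freedman (82.7% by Schoenfeld). This stands as arithmetic. It needs one particular split and an exact loss rate, and it falls short of the target by 0.2 of a point. Random allocation and chance differences in attrition will move group sizes by more than one participant whichever total is written down, so it gives no ground for calling 238 wrong.

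Two further points weaken the case for division. In a survival analysis a participant lost to follow-up is normally censored and contributes time, and perhaps an event, up to that point; counting each one as wholly lost is a worst case. And for the tumour-marker comparison the plan describes 36 as a number recruited ("The recruitment of n=36 participants into each group will enable us to detect"), so it is not clear that 36 must remain after attrition for that comparison.

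**Conclusion.** The concern does not hold. The plan's total follows exactly from a 10% addition to 216, and the 9.2% loss it covers agrees with an allowance described as approximate. If exactly 10% of those enrolled are lost, the average group of 35.7 still exceeds the 35.3 that the stated inputs require, and power stays at 80.4% or higher. The choice between 238 and 240 is one of inflation convention, worth two participants in the whole trial, 0.3 per group and about 0.3 percentage points of power. It alters no analysis and no conclusion. Stating the formula used, or rounding to 240 so that six groups divide evenly, would be tidy, but neither is needed.

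This rests on equal group sizes, on the pooled-variance normal approximation for the proportions (the plan names no test, but this method reproduces its 36), and, for the hazard ratio, on every participant having an event. The check concerns only the step from 36 per group to 238. It does not judge whether 36 per group rests on suitable survival or response assumptions.
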